9.4.2 Analysis of the Primary Efficacy Endpoint

The primary efficacy analysis is a stratified log-rank test, where stratification is according to baseline disease severity (i.e. protocol defined mild/moderate vs severe disease). Deaths will be considered as never recovering and censored at Day 29. In ACTT2, the analyses conducted will depend on the results from ACTT1 according to Table 4.

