3.3.2. Recovery and Time to Recovery

The primary efficacy outcome measure is the time to recovery. Recovery will be defined as having a value of 1, 2, or 3 on the clinical status 8-point ordinal scale. The time to recovery will be defined as the elapsed time (in days) from randomization to the earliest day at which a subject

reaches recovery. Note that since clinical status assessments are recorded as defined in Section 4.3, the day that is being assessed (not necessarily the day the response is collected) will be used to determine the timing of events. For example, a subject with a score of 5 recorded on Days 1 - 3 and a score of 3 recorded on Day 4 will have a time to recovery equal to 3 days. It is also possible that a subject has a clinical status score > 3 reported for a particular day but was subsequently discharged on the same day. Such cases will be reviewed by the NIAID Medical Officer to make the determination of whether the subject should be considered recovered in analyses. Subject data to be reviewed as part of this determination will include the reported clinical status scores while hospitalized, where the subject was discharged to (e.g. private residence, rehabilitation facility, long-term care/nursing home), and any information regarding readmittance.

Any subjects that are lost to follow-up or terminated early prior to an observed recovery will be censored at the day of their last observed assessment. Subjects who complete follow-up but do not experience recovery will be censored at the day of their Day 29 visit. All deaths within Day 29 (and prior to recovery) will be considered censored at 28 days. Note that we do not expect many subjects to worsen after discharge.

However, we will evaluate whether any discharged subjects subsequently experience a worse clinical status and sensitivity analyses will be conducted accordingly. For these analyses, subjects who recover but are later re-admitted for COVID-19 will not be considered a recovery but will instead be censored at 28 days.

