6.5. Missing Data

All attempts will be made to collect all data per protocol. Any data point that appears to be erroneous or inexplicable based on clinical judgment will be investigated as a possible outlier. If data points are identified as outliers, sensitivity analyses may be performed to examine the impact of including or excluding the outliers. Any substantive differences in these analyses will be reported.

For time to event outcomes, subjects who are lost to follow-up or terminate the study prior to Day 29 and prior to observing/experiencing the event will be censored at the time of their last observed assessment. Subjects who die prior to observing/experiencing the event will be censored at Day 29.

For the analysis of the key secondary outcome, subjects who are discharged but are subsequently re-admitted prior to Day 15 without a reported clinical score, their clinical score will be imputed at 7, which is the highest value for a hospitalized subject.

For the analyses of the secondary outcomes that involve clinical score (i.e. the key secondary outcome and time to improvement), if a subject is discharged from the hospital without a previously or concurrently reported clinical score of 1 or 2, then their clinical score at the time of discharge will be imputed as 2, which is the highest value for a non-hospitalized subject. If a subject terminates early from the study while they are hospitalized or completes the study while still hospitalized, the last observed clinical score assessment will be used as their final assessment.

For the modified version of the ordinal score described in Section 4.3, if a subject is discharged from the hospital without a previously or concurrently reported clinical score of 2 or 3, then their clinical score at the time of discharge will be imputed as 3, which is the highest value for a non-hospitalized subject.

For the analyses of the secondary outcomes described in Section 3.3, the following imputation rules will be used for subjects who are lost to follow-up, terminate early from the study, or do not have further outcome data available after discharge for any reason:

- Days of Non-invasive ventilation/high-flow oxygen:

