8. EFFICACY EVALUATION

8.1. Primary Efficacy Analysis

8.1.1. Primary Analyses

The primary analysis uses the stratified log rank test to compare treatment to control through Day 29 with respect to time to recovery, as defined in Section 3.3. Stratification is based on moderate versus severe disease at baseline. As noted in Section 3.3, all deaths within 29 days will be considered censored at Day 29 with respect to time to recovery. Conceptually, a death corresponds to an infinite time to recovery, but censoring at any time greater than or equal to Day 29 gives the same answer as censoring at Day 29; both correspond to giving deaths the worst rank.

Let MM and S denote the Moderate and Severe subgroups, respectively. The z-score associated with the stratified log rank test is

$$Z = \frac{\sum_{MM}(O_i - E_i) + \sum_S(O_i - E_i)}{\sqrt{\sum_{MM} V_i + \sum_S V_i}}$$

The sums are over recovery times t_i in the moderate and severe subgroups, O_i is the number of treatment arm participants recovering at time t_i , and E_i and V_i are the null expected value and variance of the number of treatment recoveries calculated using the hypergeometric distribution. Specifically, if n_{Ti} and n_{Ci} denote the numbers of patients 'at risk' in the two arms in a given stratum at t_i , and r_i is the total number of recoveries at t_i , then $E_i = r_i n_{Ti} / (n_{Ti} + n_{Ci})$ and $V_i = r_i (n_i - r_i) n_{Ti} n_{Ci} / [n_i^2 (n_i - 1)]$, where $n_i = n_{Ti} + n_{Ci}$. The O_i , E_i , and V_i are computed separately within the moderate and severe strata.

As noted in Section 6.6.2, to maintain an overall two-sided type-I error rate of 0.05, the Lan-DeMets spending function analog of the O'Brien-Fleming boundary will be used to derive the cumulative error spending and boundaries for the interim analysis.

For the final analysis, the log rank test will be performed using the pseudocode provided in Section 6.1. The following pseudocode can be used to compute the bounds for the final analyses and compare to the calculated log-rank statistic. The Boundaries dataset will contain the updated boundaries calculated from the interim analyses using the actual information levels observed at the interim analysis.

```

data Params_LogR;
  set logrankp(rename=(Statistic=Estimate));
  if Variable='TreatmentVariable';
  _Scale_='Score';
  _Stage_= AnalysisNumber;
  keep Variable _Scale_ _Stage_ StdErr Estimate;
run;

proc seqtest Boundary=Boundaries

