8.1.2. Supplemental and Sensitivity Analyses

For all supplemental and sensitivity analyses of the primary outcome, p-values may or may not be reported, and 95% confidence levels will be used for confidence interval estimates.

The primary analysis will be repeated in the As Treated analysis population where subjects who are not treated will be censored at enrollment. The tabular and graphical summaries described in the previous section will be replicated for this As Treated analysis.

Sensitivity analyses will be performed using Cox proportional hazards models to estimate the hazard ratio. First, an ITT analysis will be performed in which subjects who die prior to recovering are treated as experiencing a competing risk in the Fine-Gray proportional hazards regression model. Second, a Cox model will be fit with binary indicators for treatment group and disease severity Moderate vs. Severe [separate models for randomized stratum and actual stratum] as well as a treatment * disease severity interaction term. The models will be fit to the ITT analysis population. The treatment group hazard ratios and CIs will be reported for both sets of models and the interaction term p-value will be reported for the interaction models. As requested by the DSMB, a restricted mean survival time analysis will be performed as an exploratory analysis. The restricted mean recovery time estimates will be provided for each treatment group and randomized disease severity stratum as well as the difference in restricted mean recovery time between treatment groups within each of the severity strata (Table 18). Time to recovery will also be explored within prior Remdesivir treatment subgroups (Any Treatment vs. No Treatment) (Table 19).

The primary analysis will also be repeated using the other subgroups defined in Section 6.4 in place of disease severity. Each subgroup will be considered separately and the tabular and graphical summaries described in the previous section will be replicated for each subgroup. The tabular summary will also include results from an analysis of time to recovery controlling for age

and duration of symptoms as continuous covariates and baseline d-dimer and CRP values as continuous covariates. A forest plot will be generated to display the overall treatment hazard ratio estimate and CI from each of the within-stratum analyses (Table 20 and Table 21). These analyses will be performed in the ITT and As Treated populations.

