In addition, a forest plot will be generated for the “leave one out” sensitivity analyses described in Section 6.7; hazard ratio estimates and CIs will be provided for each subgroup that leaves a single site out.

An additional sensitivity analysis will evaluate the effect of recoveries that were not sustained as indicated in Section 3.3.2.

As noted in Section 6.4, analyses that take into account concomitant medication will be performed. The primary analysis will be repeated, where subjects who take prohibited medications will be treated as treatment failures and will be censored at the time of medication use.

Two corroborative summaries will also be generated. A summary of the number and percentage of subjects in each treatment group who recovered (and are alive), did not recover (and are alive), and died by Day 29 will be summarized. The summary will also include the numbers and percentages, grouping deaths and non-recoveries together (Table 24). The summaries will also be provided by the duration of symptoms categorizations specified in Section 6.4.

Other censoring techniques and additional analyses of the primary outcome may be performed.

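### The sensitivity analysis for unsustained recoveries reverses a recovery for COVID-19 readmission only, so a subject who recovers and then dies without one still counts as recovered

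*SAP*

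**What the plan says.** **Unsustained recoveries.** SAP 3.3.2 notes that "we do not expect many subjects to worsen after discharge", but undertakes to check whether any discharged subject later has a worse clinical status and to run sensitivity analyses. The rule it then gives is that "subjects who recover but are later re-admitted for COVID-19 will not be considered a recovery but will instead be censored at 28 days". SAP 8.1.2 adds nothing of its own: "An additional sensitivity analysis will evaluate the effect of recoveries that were not sustained as indicated in Section 3.3.2". The title and footnote planned for Table 22 (SAP Appendix 1) are likewise confined to COVID-19 readmission.

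**Deaths.** SAP 3.3.2: "All deaths within Day 29 (and prior to recovery) will be considered censored at 28 days". SAP 6.5: "Subjects who die prior to observing/experiencing the event will be censored at Day 29". SAP 8.1.1, with a reference back to Section 3.3: "all deaths within 29 days will be considered censored at Day 29 with respect to time to recovery". Protocol Appendix B 9.4.2: "Deaths will be considered as never recovering and censored at Day 29". The competing-risk analysis in SAP 8.1.2 is one in which "subjects who die prior to recovering are treated as experiencing a competing risk in the Fine-Gray proportional hazards regression model".

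**Table 24.** The SAP 8.1.2 text describes three groups by Day 29: recovered and alive, not recovered and alive, and dead. The programming note in Appendix 1 places a subject who recovers and later dies under both Recovered and Deaths. If any such subject occurs, it requires a footnote giving their number.

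**The concern.** The readmission row exists to show whether the treatment effect survives once recoveries that did not last are removed. Death is score 8 on the scale in SAP 3.2, and so the plainest case of a recovery that did not last, yet the rule does not reach it. Three kinds of subject slip through: one who dies at home after discharge, one who dies during an admission for something other than COVID-19, and one who reaches score 3 in hospital, deteriorates and dies. The last was never discharged, so cannot be readmitted and falls outside even the broad opening sentence of SAP 3.3.2.

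If such deaths were more frequent in one arm, the row would present as robust a ratio that still counts those subjects as treatment successes. The other points concern wording. Two statements of the death rule omit the limit to deaths before recovery, and the Table 24 text and its note define the Recovered group differently.

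**Working it through.** **1. The plan's own figure.** SAP Section 5 uses E = 4(1.96 + z_β)² / (ln θ)² with θ = 1.25 and 85% power. With z_β = 1.04, E = 4 × 3.00² / 0.2231² = 36 / 0.0498 = 723; the unrounded z_β gives 721.3. N = 723 / 0.70 = 1032.9. The stated 723 and 1032 are reproduced, and nothing below changes them.

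**2. Tracing one subject.** Take a subject who recovers on Day 8 and dies on Day 20 with no COVID-19 readmission.
- Primary analysis (SAP 3.3.2, 8.1.1): recovery on the first qualifying day; the death comes after the event, so the 3.3.2 death rule does not apply.
- Fine-Gray (8.1.2): the competing event is death before recovery, so this is a recovery.
- Readmission row (Table 22): no COVID-19 readmission, so a recovery.
- Interaction, covariate-adjusted, subgroup, leave-one-site-out and restricted-mean analyses: these take the recovery event from 3.3.2, so a recovery.
- Medications-of-interest analysis (SAP 6.4): changes recovery only through medication use, not through death.

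No specified time-to-recovery analysis reverses this recovery because of the death. Had a COVID-19 readmission preceded the death, Table 22 would have reversed it.

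**3. Which death rule is meant.** SAP 3.3.2 and 6.5 limit the rule to deaths before the event; SAP 8.1.1 and protocol Appendix B 9.4.2 do not say so. Three things settle the reading. SAP 8.1.1 refers to Section 3.3. The endpoint is the first day in a recovered category. The Table 24 note counts recovered-then-died subjects as recovered. Day 29 and 28 days are the same point, since Day 1 is the day of randomization.

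**4. Possible size.** The documents give no count of deaths after recovery. Assume 0.5% to 2% of 723: 0.005 × 723 = 3.6 and 0.02 × 723 = 14.5, so about 4 to 14 subjects.

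Loss of events alone matters little. Approximate power is Φ(ln 1.25 × √d / 2 − 1.96):
- d = 723: Φ(3.000 − 1.96) = 85.1%
- d = 723 − 14 = 709: Φ(2.971 − 1.96) = 84.4%

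For imbalance, an unstratified log-rank simulation was run. Its assumptions: 516 per arm, exponential recovery times, daily assessment, pooled 70% recovered by 28 days, rate ratio 1.25, 2000 runs. Reversed subjects were drawn at random from those recovered and kept at risk to 28 days. Mean Z with none reversed was 2.98. The last column is the two-sided binomial probability, at equal risk in both arms, of a split at least that uneven.

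| Reversed, baricitinib/control | Change in Z | Change in log ratio | Ratio, from 1.25 | Probability |
|---|---|---|---|---|
| 2/2 | −0.01 | −0.0002 | 1.25 | – |
| 3/1 | −0.14 | −0.010 | 1.24 | 0.63 |
| 4/0 | −0.27 | −0.020 | 1.23 | 0.13 |
| 0/4 | +0.25 | +0.020 | 1.28 | 0.13 |
| 7/7 | −0.04 | −0.001 | 1.25 | – |
| 9/5 | −0.29 | −0.020 | 1.22 | 0.42 |
| 10/4 | −0.42 | −0.030 | 1.21 | 0.18 |

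For example, exp(ln 1.25 − 0.0303) = 1.213. The shift can go in either direction.

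**The case against.** The case for leaving the plan alone has several parts.

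- **Scope.** The opening sentence in SAP 3.3.2 is broad enough to include death, and SAP 8.1.2 allows further censoring techniques. This stands as permission, but neither passage specifies an analysis. A row fixed in advance is better evidence than one chosen after unblinding.
- **Other coverage.** Deaths enter the mortality, safety and Day 15 analyses, and status is tabulated by arm at Days 22 and 29. True, but none of these gives the recovery rate ratio with those recoveries removed. The Medical Officer review in SAP 3.3.2 concerns scores above 3 on the day of discharge, not later death. The manufacturer's Addendum SAP (SAP 2.1) may address intercurrent events, but it is not among the documents.
- **Preference.** Adding all-cause death to a COVID-19-specific rule is partly a choice of what to estimate. That is a reason to keep the readmission row and add to it, not replace it.

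A reader might also infer more than the documents support. One inference is that the protocol and SAP truly conflict, so that the primary analysis is undefined for these subjects. The reference to Section 3.3, SAP 6.5 and the Table 24 note show that deaths before recovery are meant. Another is that Table 24 conceals the overlap, but its note requires a footnote with the count. A third is that the fourth column leaves these subjects unplaced. Its label, Not Recovered or Died, and the SAP 8.1.2 text grouping deaths with non-recoveries put them there.

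**Conclusion.** The gap is real and minor. The analysis intended to remove unsustained recoveries omits death after recovery unless a COVID-19 readmission came first. The primary test, the 723 recoveries and the sample size are unaffected, and Table 22 carries no p-values. On the assumed 4 to 14 subjects, balanced deaths change almost nothing and the 10/4 split moves the ratio by about 0.04; only imbalance between arms would make the row informative. That range is an assumption, and the simulation ignores stratification and any link between time of recovery and later death.

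The death-rule wording and the Table 24 mismatch are editorial. The intended meaning of the first can be recovered from the SAP itself, and what remains of the second is that the text calls a group alive while the note includes subjects who died.

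**What to change.** 1. Keep the COVID-19 readmission row in Table 22. Add a second row in which a subject who recovers and then dies from any cause by Day 29 is also not a recovery and is censored at 28 days. Word it to include subjects who reached score 3 and were never discharged, and add the matching sentence to SAP 3.3.2.
2. In SAP 8.1.1, state that the death rule applies to deaths before recovery, and record that protocol Appendix B 9.4.2 is read the same way.
3. For Table 24, either drop the alive qualifier from the SAP 8.1.2 text or make the three groups exclusive. In both cases give the footnote already required by arm. If the groups are made exclusive, note that Recovered will fall below n in Table 15 by the number of deaths after recovery.

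The cost is one supplementary row with slightly fewer recoveries, and a few words of text. No new data are needed: deaths are recorded on the ordinal scale (protocol Appendix B 8.1.2.2), date and cause of death are secondary endpoints (SAP 3.2), and mortality is asked about at phone visits (Appendix B 1.2, note 9).

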3.3.3. Clinical Status at Specific Timepoints

The key secondary analyses include evaluation of the clinical status score at Day 15. For this outcome, Study Visit Day 15 is the timepoint of interest, not necessarily the actual study day. The score collected at the study visit corresponding to Day 15 will be used for this outcome. For analyses of this outcome, imputation of the clinical score may be performed following the rules described in Section 6.5.

Additional analyses are clinical status at Days 3, 5, 8, 11, 15, 22, and 29. As the with above, the scores that will be used are those collected at the study visits corresponding to those days.

3.3.4. Time to Clinical Status Improvement

Additional analyses will evaluate the time to improvement of at least one point on the clinical status 8-point ordinal scale. That is, improvement will be defined as a decrease of at least one point on the 8-point scale compared to the baseline value (e.g. from 5 to 4; from 5 to 3) and the time to improvement will be defined as the elapsed time (in days) from randomization to the earliest day of observed improvement. Note that since clinical status assessments are recorded as defined in Section 4.3, the day that is being assessed (not necessarily the day the response is collected) will be used to determine the timing of events.

For analyses of this outcome, imputation of the clinical score may be performed following the rules described in Section 6.5.

Any subjects that are lost to follow-up or terminated early prior to an observed improvement will be censored at the day of their last observed assessment. Subjects who complete follow-up but do

not experience improvement will be censored at the day of their Day 29 visit. All deaths within Day 29 (and prior to improvement) will be considered censored at 28 days.

An alternative definition of improvement will also be used where improvement will be defined as a decrease of at least two points on the 8-point scale compared to the baseline value (e.g. from 5 to 3; from 5 to 2). The timing and censoring definitions will follow similarly to the above.

3.3.5. Time to Discharge or NEWS of ≤ 2

The time to discharge or NEWS of ≤ 2 will be defined as the elapsed time (in days) from baseline to the earliest day at which either of the following occur:

- Discharge from hospital
- Reported NEWS of ≤ 2 which is maintained for 24 hours

For the latter bullet, to meet this criterion, scores of ≤ 2 must be reported on consecutive study visits. The timing of the event will be set to the day of the second assessment.

All deaths that occur before discharge or before an observed NEWS of ≤ 2 will be considered censored at 28 days.

3.3.6. Days of Non-invasive ventilation/high-flow oxygen

Non-invasive ventilation/high flow-oxygen days will be defined as the number of days where the clinical status score is equal to 6. After discharge, the Post-Discharge Supplemental Oxygen CRF questions regarding days of non-invasive ventilation or high-flow oxygen will be used. The total number of days will be the sum of all reported days, regardless of whether the days occur consecutively or in disjoint intervals. See Section 6.5 for the plan for handling subjects who do not have data through Day 29 or die prior to Day 29.

3.3.7. Days of Invasive Mechanical Ventilation/ECMO

Invasive Mechanical Ventilator / ECMO days will be defined as the number of days where the clinical status score is equal to 7. After discharge, the Post-Discharge Supplemental Oxygen CRF questions regarding days of ECMO or invasive ventilation will be used. The total number of days will be the sum of all reported days, regardless of whether the days occur consecutively or in disjoint intervals. See Section 6.5 for the plan for handling subjects who do not have data through Day 29 or die prior to Day 29.

3.3.8. Days of Oxygen

Oxygen days will be defined as the number of days where the clinical status score is equal to 5, 6, or 7. After discharge, the Post-Discharge Supplemental Oxygen CRF question regarding days of oxygenation (including ECMO, invasive ventilation, non-invasive ventilation, high-flow oxygen devices, and all other oxygen delivery devices) will be used. The total number of days will be the sum of all reported days, regardless of whether the days occur consecutively or in disjoint intervals. See Section 6.5 for the plan for handling subjects who do not have data through Day 29 or die prior to Day 29.

